10 SAFETY AND TOLERABILITY ANALYSES

Safety outcomes include:

- Solicited AEs (including solicited local injection site pain, redness, and swelling and solicited general body symptoms such as headache, fatigue /tiredness, stomach problems, and fever).
- Unsolicited AEs
- All SAEs
- Vaccination-related SAEs (serious adverse drug reactions [ADRs]).

- AEs of special interest through 6 month post vaccination
- Laboratory safety tests
- Pregnancy outcomes

10.1 Adverse Events

AEs will be coded using Medical Dictionary for Regulatory Activities (MedDRA) version 22.0 or higher.

AE severity will be graded using the Division of Acquired Immune Deficiency Syndrome (DAIDS) Table for Grading for Intensity (Severity) of Adult and Pediatric Adverse Events Version 2.1, July 2017 as Grade 1 (Mild), Grade 2 (Moderate), Grade 3 (Severe) or Grade 4 (Potentially Life-threatening) on the eCRF.

The following reporting windows are applicable for AEs:

AE Category	Reporting Window
Solicited	Through 7 days post vaccination
Unsolicited	Through 28 days post vaccination
SAEs and AESI	Through 6 months post vaccination
Serious related AEs [ADRs]	Through the end of the study

Only AEs within the reporting window will be included within the relevant category in summary tables. All AEs will be listed, regardless of if it was reported within the applicable reporting window.

Adverse events of special interest (AESIs) are AEs that the sponsor wants to monitor carefully. The following AEs will be collected and reported and summarized as AESIs:

System Organ Class	Preferred Term
Immune system disorders	Anaphylactic reaction
General disorders	Disseminated BCG disease
Infections and Infestations	Osteomyelitis
	Suppurative lymphadenitis
	Injection site abscess
Skin and subcutaneous tissue disorders	Injection site lupus vulgaris

	Injection site keloid formation
Bone disorders	Osteitis

An AE overview table will be generated containing the frequency and percent of participants with at least 1 event as well as total number of reported events in each of the following categories (summarized by treatment group) and also the 95% CI (calculated for a single proportion using mid-p binomial option [refer to Appendix 7]):

- Any AE.
- Unsolicited AEs.
- Related AEs.
- Grade 1 AEs.
- Grade 2 AEs.
- Grade 3 or higher AEs.
- Related, Grade 3 or higher AEs.
- AEs leading to premature study discontinuation.
- AEs of special interest (AESI).
- SAEs.
- SAEs with outcome of death.
- Serious adverse drug reactions (ADRs).

Additionally, the following will be summarized by System Organ Class (SOC) and by preferred term (PT), for each treatment group:

- Incidence of AEs.
- Incidence of AEs by highest grade.
- Incidence of SAEs.
- Incidence of serious ADRs.
- Incidence of unsolicited non-serious AEs.

• AESIs

Summaries of AEs by SOC and PT will be sorted alphabetically by SOC and by decreasing frequency of PT in the BCG treatment group. If a participant has more than one AE at a given level (e.g. SOC and PT), the participant will only be counted once within that level. Missing severity grade and relationship will not be regarded as 'worst case' and will be reported as missing values in the summary tables.

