8.3. Adverse Events and Serious Adverse Events

The definitions of AEs, SAEs, serious ADRs, SUSARs, and adverse events of special interest (AESIs) can be found in Appendix 2, Section 10.2.1, and 10.2.2, 10.2.3, 10.2.4, respectively.

AEs will be reported by the participant (or, as appropriate, the participant's legally authorized representative). Biochemistry and/or hematology findings may also qualify as AEs if the investigator considers them as such.

SAEs that the investigator assessed as related to vaccination will be collected throughout the study.

Study nurses and physicians are responsible for collecting and documenting information and events that would potentially meet the definition of an AE. However only the investigator (study physician) is responsible for assessment, including assignment of causality and intensity, reporting and management of all AEs. The investigator is responsible for following up AEs that are serious, considered related to the study intervention or study procedures, or that caused the participant to discontinue the study (Section 7).

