8.3.1. Time Period and Frequency for Collecting AE and SAE Information

Type of Event	Collection Time Period
All solicited AEs	Day 1 through Day 7 (inclusive)
Unsolicited AEs	Screening through Day 28 (inclusive)*
All SAEs and AESIs	Screening through Month 6*
Serious ADRs	Day 1 through the end of the study

*Refer to the SoA, Section 1.3 for collection of AEs from time of signed consent.

Distribution and collection days for diary cards are shown in the SoA (Section 1.3).

Medical conditions that begin before the start of study intervention but after obtaining informed consent will be recorded on the Medical History/Current Medical Conditions section of the CRF, not the AE section.

All SAEs and AESIs will be reported to the sponsor or designee within 24 hours, as indicated in Appendix 2, Section 10.2.6. The investigator will submit any updated SAE data to the sponsor or designees within 24 hours of it being available.

Investigators are not obligated to actively seek AEs or SAEs after conclusion of study participation. However, if the investigator learns of any SAE, including a death, at any time after a participant has been discharged from the study, and he/she considers the event to be related to the study intervention or study participation, the investigator must notify the sponsor or designee within the same 24 hours timeline.

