8.3.5. Death Events

Any untoward medical occurrence resulting in death is reported as an SAE. The cause of death will be appropriately documented in the SAE report form and supporting evidence will be provided.

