4.4 Safety Endpoints

Safety outcomes include:

- Solicited AEs through 7 days post vaccination (based on the review of diary card data),
- Unsolicited AEs through 28 days post vaccination,
- SAEs through 6 month post vaccination,
- AEs of special interest through 6 month post vaccination
- Serious adverse drug reactions (ADRs) through the entire study duration
- Laboratory safety tests
- Pregnancy outcomes
- SARS-CoV-2 serostatus

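### Deaths judged unrelated after Month 6 have no planned by-arm summary in the SAP's adverse event tables

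*SAP*

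**What the plan says.** **Analysis.** The window table in SAP 10.1 sets the period for SAEs and AESIs at "Through 6 months post vaccination" and runs serious related events to the end of the study. The filter follows: "Only AEs within the reporting window will be included within the relevant category in summary tables". The next sentence keeps everything in the listings: "All AEs will be listed, regardless of if it was reported within the applicable reporting window". The AE overview table has a row "SAEs with outcome of death" and a separate row for serious ADRs. SAP 4.4 confirms the longer period for related events: "Serious adverse drug reactions (ADRs) through the entire study duration".

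**Collection.** Protocol 8.3.1 collects all SAEs and AESIs "Screening through Month 6", and Protocol 10.2.6 sets the same six-month limit for reporting them to the sponsor. After that, Protocol 8.3 keeps only the related ones: "SAEs that the investigator assessed as related to vaccination will be collected throughout the study". Protocol 9.4.2 uses the same two periods for analysis.

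**Deaths.** Protocol 8.3.5 says: "Any untoward medical occurrence resulting in death is reported as an SAE". It gives no period and does not refer to 8.3.1.

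**The concern.** The trial follows adolescents for 48 months after a live vaccine or placebo. All-cause mortality by arm is a basic safety summary, and it needs no causality judgement. As planned, the fatal-event row stops at Month 6. From then on, the investigator's view of relatedness decides whether a death must be collected as an SAE and whether it reaches an AE table.

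That judgement is made at sites that Protocol 4.1 and 6.3.2 expect to learn the allocation of many BCG recipients once a lesion develops. The sponsor can upgrade a reported event to related (Protocol 8.3.3.2), but not one it never received. A site facing an unrelated death at Month 30 would also find 8.3.1 and 8.3.5 pointing in different directions on whether to report it.

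**Working it through.** The plan states no figure for this point, so there is none to reproduce. The check has two parts.

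**1. Where a death between Month 6 and Month 48 appears**

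| Output or rule | Judged related | Judged unrelated |
|---|---|---|
| Required as an SAE under Protocol 8.3.1 and 10.2.6 | Yes, as a serious ADR | No |
| Protocol 8.3.5 | Classed as an SAE | Classed as an SAE; period not stated |
| SAP 10.1 fatal-event row | Outside the SAE window on a literal reading | Outside the window |
| SAP 10.1 serious ADR tables | Counted by arm, but not identified as fatal | Not counted |
| SAP 10.1 listings | Listed | Listed only if collected |
| SAP 8.1 disposition | Depends on the eCRF categories | Depends on the eCRF categories |

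The unrelated column contains no assured count by arm.

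**2. How much follow-up lies outside the fatal-event row**

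Inputs: window of 6 months (SAP 10.1); follow-up of 48 months (Protocol 4.3); 1800 randomized and 5% average annual loss (Protocol 9.2).

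- Calendar share inside the window: 6/48 = 12.5%. Outside: 42/48 = 87.5%.
- Person-years to time t (in years), with constant annual retention of 0.95: PY(t) = 1800 × (1 − 0.95^t) / (−ln 0.95), where −ln 0.95 = 0.05129.
- PY(0.5) = 1800 × 0.02532 / 0.05129 ≈ 889.
- PY(4) = 1800 × 0.18549 / 0.05129 ≈ 6509.
- Share inside the window: 889/6509 = 13.7%. After Month 6: about 5621 person-years, or 86%.
- At the maximum of 2150 randomized (Protocol 7.4.2), the figures are about 1061 of 7775 person-years, the same share.

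**Illustration only.** The documents give no mortality rate. For an assumed range of 0.2 to 2 deaths per 1000 person-years, both arms together:

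- up to Month 6: 889 × 0.0002 ≈ 0.2, to 889 × 0.002 ≈ 1.8;
- after Month 6: 5621 × 0.0002 ≈ 1.1, to 5621 × 0.002 ≈ 11.2.

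An unknown part of the later deaths would be judged related and so already be counted as serious ADRs.

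**The case against.** The strongest reply is that this is a deliberate and consistent design. The two periods, all SAEs to Month 6 and related SAEs to the end, appear in the objectives and endpoints, Protocol 8.3.1, 9.4.2 and Table 10, and SAP 4.4 and 10.1. The vaccine is licensed, and Protocol 8.3.4 runs regulatory reporting on a post-marketing model. The SAP applies what the protocol sets. All of this stands, so SAP 10.1 does not depart from the protocol.

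A reader might infer that 8.3.5 and 8.3.1 flatly contradict each other. The documents do not establish that. Section 8.3.5 can be read as a statement of seriousness that operates inside the 8.3.1 periods. Protocol 10.3 does this openly for abnormal pregnancy outcomes: it calls them SAEs and then applies the 8.3.1 periods. For events learned of after discharge, 8.3.1 itself puts deaths under the relatedness condition. What remains is that 8.3.5 does not say which reading applies. Protocol 10.2.5 asks for any available post-mortem findings on a death during participation, which suggests that later deaths were expected to be documented.

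A reader might also infer that every death after Month 6 drops out of the safety output. That is not so either. Related fatal events are tabulated to the end of study, collected late events are listed, and SAP 10.9 counts suspected and confirmed TB by arm over the whole study, though not TB deaths. These outputs narrow the gap without closing it. A listing shows only what was collected and is not a count by arm. The serious ADR tables do not mark an event as fatal. Disposition may show deaths, but neither document says that death is one of the recorded reasons for leaving the study.

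**Conclusion.** The point holds as a gap in safety reporting: deaths judged unrelated after Month 6 have no planned AE summary by arm and need not be collected as SAEs under 8.3.1. The fatal-event row covers 12.5% of scheduled follow-up, or about 14% of person-time if loss runs at the planned 5% a year. This rests on reading the row as an ordinary SAE category, which is the literal reading because the SAP gives it no other period.

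How many deaths would be missed cannot be stated, since the illustrative counts depend wholly on the assumed rate. The documents do not support calling the SAP wrong as written, and neither the primary efficacy test nor its error rate is affected. The change is worth making because it is cheap and because an all-cause count does not depend on a relatedness judgement by site staff who may know the allocation.

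**What to change.** - **SAP 10.1:** exempt fatal events from the reporting-window filter, and state that the fatal-event row runs to the end of study. Add one table by arm of deaths from any cause, Day 1 through end of study, with cause (TB or other).
- **Protocol 8.3.1 and 8.3.5:** reconcile the two, by adding a collection row for deaths from any cause through end of study and a cross-reference from 8.3.5. Make 10.2.6 agree.
- **Leave as is:** the Month 6 limit for other unrelated SAEs.

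The cost is one SAP sentence, one table and one protocol row. The added burden on sites should be small, because Protocol 7.2 already has them record the time of and reason for withdrawal.

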10.2 Reactogenicity Data

Reactogenicity data is used synonymously with solicited AEs. The reactogenicity data collected from the paper diary will include: injection area symptoms (pain at injection site, redness and swelling), general body symptoms (headache, tiredness, stomach problems, temperature), and use of medication.

The paper diary will record reactogenicity data from Day 1 to Day 7 following vaccination. The analysis interval for reactogenicity data will be 'Any Day 1 to 7' which includes data from Day 1 to Day 7. The day of vaccination is considered as Day 1.

The diary card is used to record duration and intensity/severity (Grade 1 to 4) and largest diameter in mm of the red and swollen area of solicited injection area symptoms and general body symptoms AEs for 7 days following vaccination.

Reactogenicity data will be presented for the Safety population. The number of participants who returned the diary card, including the reason for not returning the diary card will be summarized. Participants reporting any symptoms (for both injection area symptoms and general body symptoms) on each day after vaccination will be summarized.

A listing for the diary card data will be displayed for the Safety population. Participants reporting any symptoms (for both injection area symptoms and general body symptoms) on each day after vaccination will be summarized.

The following additional summaries will be presented for the Safety population:

10.2.1 Injection Area Symptoms

The proportion of participants reporting each injection area symptom will be presented by treatment group for the safety population. For each injection area symptom, the determination of whether or not the specific symptom occurred on each day and 'Any Day 1 to 7' will be made.

For the 'Any Day 1 to 7' summary tables, the derivation of the proportion is calculated as n1/(n1+n2) where

- n1: Any Day 1 to 7 participant reports the symptom as 'mild', 'moderate' or 'severe' on any Day 1 to 7.
- n2: Participant reports the symptom as 'none' on all 7 days or as a combination of 'none' and missing on all 7 days.

Participants that report the symptom as missing on all 7 days are not included in the proportion calculations.

For redness and swelling, 'mild', 'moderate', and 'severe' categories are based on the largest diameter of the redness or swelling reported in mm and they are age-group specific:

- for participants >15 years: Mild 25 to <50mm; Moderate >=50 to <100 mm; Severe >=100 mm;
- for participants <=15 years: Mild 0 to <=25mm; Moderate >25 to <50 mm; Severe >=50 mm

(refer to the 'Site Reactions to Injections and Infusions' table in Appendix 5 of the study protocol which is based on the Division of AIDS Table for Grading the Intensity [severity] of Adult and Pediatric Adverse Events Version 2.1, July 2017). For participants > 15 years old, 'none' = largest diameter reported on the diary card<25 mm.

95% CI based on the conditional binomial Clopper-Pearson method with mid-p correction (refer to Appendix 7) will be provided.

The maximum severity (highest grading) of each local reaction within 7 days of vaccination will be derived as follows:

- =., if values are missing for all Days 1 to 7.
- =0, if the participant reports all reactions as 'None' or a combination of missing and none for all Day 1 to 7.
- =highest grade (maximum reported severity) within 7 days of vaccination if the answer is not 'None' for at least 1 day.

Results will be summarized for each local reaction reporting n (%) participants by maximum severity within each age group (>15 years and <=15 years).

Duration and Onset Day of Injection Area Symptom:

For participants experiencing any injection area symptom, the onset day (first day of the injection area symptom reported via diary relative to the vaccination) and the maximum duration (last day of symptom – first day of symptom + 1) will be derived. Resolution of the event is the last day in which the event is recorded in the diary or the date the event ends if it is unresolved during the participant diary-recording period.

The following summary results will be generated for injection area symptoms within 7 days after vaccination:

• number and percentage of participants with injection area symptom (any severity) and by severity grade

- number and percentage of participants with any injection area symptom within 7 days after vaccination
- number and percentage of participants by injection area symptom onset day
- number and percentage of participants by injection area symptom duration (number of days)
- for each injection area symptom: mean, median, Q1-Q3, and min-max for symptom duration.

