8.2.4. Diary Card and Daily Temperature Monitoring

On Day 1, participants will be given a diary card and receive guidance on how to fill in the card. Participants will also receive a digital thermometer.

The diary card will be used by the study participants or parent or guardian/LAR to record the duration and intensity (Grade 1, 2, 3, or 4) of solicited local and general AEs for 7 days following vaccination. The diary card will also allow for unsolicited AEs to be recorded.

The diary card will be collected and reviewed by the PI (or designee) on Day 8. No changes to the diary card will be permitted; however, any verbally recalled information provided by the participant or parent or guardian/LAR during review of the diary card will be documented in the source document and reported as an AE, as applicable. Any participant-reported Grade 4 event will be assessed by the investigator.

A memory aid will be distributed to the participant at the Day 8 visit and the participant will be instructed to record unsolicited adverse events using the aid. The memory aid will be collected at the Day 29 visit.

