10.2.2 General Body Symptoms

For each general body symptom event recorded on the diary, the following summaries and analyses will be presented similarly to injection area symptoms:

- Each general body symptom on each day (up to Day 7) after vaccination
- Each general body symptom event on 'Any Day 1 to 7' after vaccination
- Maximum severity of each general body symptom event on 'Any Day 1 to 7' after vaccination
- Maximum duration of each general body symptom after vaccination
- Any general body symptom event (including fever) on 'Any Day 1 to 7' after vaccination

Grading for fever is as follows: Mild=38.0 to <38.6°; Moderate>=38.6 to <39.3°C; Severe>=39.3 to <40.0°C; Life-threatening>=40°C. The derivation of these variables is similar to the derivation of the variables for injection area symptoms.

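### The SAP's 'Any Day 1 to 7' proportion for solicited symptoms leaves out Grade 4, so a participant whose only report of injection site pain is Grade 4 falls out of both numerator and denominator

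*SAP*

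**What the plan says.** SAP 10.2.1 sets out the seven-day summary: "the derivation of the proportion is calculated as n1/(n1+n2) where" n1 counts a participant if the "participant reports the symptom as 'mild', 'moderate' or 'severe' on any Day 1 to 7". n2 is defined by "Participant reports the symptom as 'none' on all 7 days or as a combination of 'none' and missing on all 7 days". One exclusion is named: "Participants that report the symptom as missing on all 7 days are not included in the proportion calculations".

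The scale being summarised has four levels. Protocol 8.2.4 has the diary "record the duration and intensity (Grade 1, 2, 3, or 4) of solicited local and general AEs for 7 days following vaccination", and SAP 10.2 describes the same range of grades. Protocol 8.2.4 also provides for the top grade being reported: "Any participant-reported Grade 4 event will be assessed by the investigator". Protocol Appendix 5 has separate Grade 4 definitions for injection site pain, headache and fatigue.

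For general body symptoms, SAP 10.2.2 lists a fourth fever category, "Severe>=39.3 to <40.0°C; Life-threatening>=40°C", and then says that the variables are derived in a similar way to those for injection area symptoms.

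**The concern.** The two terms of the proportion should together cover every participant with at least one non-missing entry. They do not. A Grade 4 entry is neither mild, moderate or severe, nor 'none'. A participant with one or more Grade 4 days and otherwise only 'none' or missing entries therefore has no place in the calculation, and the exclusion rule does not account for the loss.

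Solicited AEs through seven days are a secondary safety endpoint, and Protocol 9.4.2 plans their incidence by arm with 95% confidence intervals. The written rule can only lower that incidence, and it loses only participants whose sole positive reports carry the highest grade. It also makes the SAP inconsistent with itself. The maximum-severity rule in 10.2.1 keeps the highest grade whenever an answer is not 'none', and the list of summaries at the end of 10.2.1 counts symptoms of any severity. Two programmers following different parts of the same section would report different counts and denominators from the same diary data.

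**Working it through.** The plan states no figure for this rule, so there is nothing to reproduce. The check has two parts.

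**1. Does the rule classify every diary?** Give each of the seven days one of six values: missing, none, or Grade 1, 2, 3 or 4. That makes 6^7 = 279,936 patterns. Apply SAP 10.2.1 as written:

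| Class | Condition | Patterns |
|---|---|---|
| n1 | at least one Grade 1, 2 or 3 day | 6^7 − 3^7 = 279,936 − 2,187 = 277,749 |
| n2 | only none, or none and missing | 2^7 − 1 = 127 |
| Stated exclusion | missing on all seven days | 1 |
| Unclassified | at least one Grade 4 day, otherwise only none or missing | 3^7 − 2^7 = 2,187 − 128 = 2,059 |

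The four classes sum to 279,936. A full enumeration gave the same counts. They show where the gap lies, not how often it would occur, because the patterns are not equally likely. A participant with Grade 4 on one day and Grade 1 to 3 on another stays in n1.

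**2. How far does the rate move?** Let N be the participants in an arm with at least one entry, x those with any Grade 1 to 3 day, and k those whose only positive entries are Grade 4.

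- As written: x/(N − k)
- With Grade 4 counted in n1: (x + k)/N
- Shortfall: (x + k)/N − x/(N − k) = k(N − k − x)/[N(N − k)], which is never negative

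N = 900 is the planned size per arm (Protocol 9.2), with every diary assumed to have at least one entry. The documents give no x or k, so these are assumed and shown over a range:

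| x | k | As written | Grade 4 counted |
|---|---|---|---|
| 0 | 3 | 0/897 = 0.00% | 3/900 = 0.33% |
| 9 | 1 | 9/899 = 1.00% | 10/900 = 1.11% |
| 9 | 9 | 9/891 = 1.01% | 18/900 = 2.00% |
| 90 | 1 | 90/899 = 10.01% | 91/900 = 10.11% |
| 90 | 3 | 90/897 = 10.03% | 93/900 = 10.33% |
| 90 | 9 | 90/891 = 10.10% | 99/900 = 11.00% |
| 450 | 9 | 450/891 = 50.51% | 459/900 = 51.00% |

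The absolute shift is at most k/N. It matters in relative terms only when the symptom is otherwise rare.

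**Which symptoms are exposed?** Injection site pain is exposed directly. Headache, tiredness, stomach problems and fever of 40°C or more are exposed only if 10.2.2 imports the three-level n1. Redness and swelling are not exposed: 10.2.1 grades them by diameter with no upper limit on the severe class, so no measured diameter can lie above it.

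**The case against.** The strongest reply is that this is incomplete wording and not a chosen analysis. SAP 10.2.1 begins by asking whether the symptom occurred at all, and it names one exclusion, which is not Grade 4. The intent was very probably any grade. I accept that, but the text is what gets programmed, and as written it gives a wrong proportion and contradicts other summaries in the same section.

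Three stronger readings are tempting, and the documents do not support them.

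- A reader might infer that an imbalance between arms in Grade 4 reports would be invisible. It would not. Grade 4 reaches the maximum-severity tables (10.2.1 and 10.2.2), the by-grade summary of injection area symptoms, the diary listing (10.2) and the IDMC tables by maximum severity (4.2.3). Protocol 8.2.4 also sends each such report to the investigator.
- A reader might infer that the SAP rules out a single reading of 40°C or more as fever. SAP 10.2.2 says only that the derivation is similar, and it lists the life-threatening category in the same paragraph. Counting all four categories is a natural reading. The text is ambiguous for fever, and no explicit rule excludes it.
- A reader might infer a large understatement. That needs many Grade-4-only participants relative to other reporters, and nothing in the documents supports such a count. A participant who also has a lower-grade day is retained, so the number lost is probably small.

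**Conclusion.** The point stands as a minor defect in one definition. For injection site pain, the literal 'Any Day 1 to 7' proportion drops Grade-4-only participants from both its terms, which biases the rate downward and puts it at odds with the maximum-severity and any-severity summaries. For headache, tiredness, stomach problems and fever, the same follows only if the similar derivation in 10.2.2 is taken to include the three-level n1. Redness and swelling are unaffected.

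The error is confined to this proportion and its confidence interval. On the assumed counts of 90 Grade 1 to 3 reporters and 1 to 9 Grade-4-only participants among 900, the shortfall is between 0.10 and 0.90 percentage points. The true size depends on a Grade 4 rate that the documents do not give. The conclusion also rests on participants being able to enter Grade 4 in the diary, which both documents say they can.

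**What to change.** In SAP 10.2.1, define n1 as a report of any Grade 1 to 4 (mild, moderate, severe or potentially life-threatening) on any of Days 1 to 7. In SAP 10.2.2, state that the same definition applies to the general body symptoms, and that fever in the life-threatening category is included. All 2,059 unclassified patterns then move into n1, only the all-missing diary stays out, and the proportion agrees with the maximum-severity and any-severity summaries.

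No Grade 4 row is needed for redness or swelling, where it would be empty by construction. The cost is a few words in two subsections. No new data are needed, and no study procedure changes.
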